10.6 Randomization

The participants will be randomized using permuted block randomization in a 3:1 ratio to the two arms of the study. Study arm randomization will be stratified by site to ensure balanced assignment for products at each site. The randomization scheme will be generated and maintained by the MTN SDMC.

10.7 Blinding

Study staff and participants will be blinded to the random treatment assignment of all study participants. All study product will be packaged in identical individual wrappers. Blinding will be maintained until all data are entered into the study database, all study endpoint data and other data included in the final analysis have been cleaned and verified, and the data are ready for final analysis. This will be explained to participants as part of the study.

There are no circumstances under which it is expected that unblinding will be necessary for the provision of medical treatment or to otherwise protect the safety of study participants. As described in Section 7.5.4, in the event that an investigator is concerned that a participant might be put at an increased risk by continuing product use, the Investigator may discontinue study product use by this participant; however, knowledge of the specific product to which the participant was assigned should not be necessary to guide further follow-up and/or treatment. If an Investigator feels that specific product knowledge is necessary to protect participant safety, the Investigator will notify the PSRT to review and approve the request.

10.8 Data and Safety Monitoring and Analysis

10.8.1 Study Monitoring Committee

Data and Safety Monitoring Board oversight is not planned for this study. The MTN SMC will conduct interim reviews of study progress, including rates of participant accrual, retention, completion of primary and main secondary endpoint assessments,

study or lab issues, and a closed safety data report to voting SMC members. The review will take place at least once during the study, and as needed. At the time of this review, or at any other time, the SMC may recommend that the study proceed as designed, proceed with design modifications, or be discontinued. For further information regarding the SMC, please reference the MTN Manual of Operational Procedures (www.mtnstopshiv.org).

10.8.2 Primary Analysis

When the use of descriptive statistics to assess group characteristics or differences is required, the following methods will be used: for categorical variables, the number and percent in each category; for continuous variables, the mean, median, standard deviation, quartiles and range (minimum, maximum). Within-treatment group assessment of the change from the baseline measurement to a follow-up measurement will be analyzed using McNemar's test (for categorical response variables) or the paired t-test or Wilcoxon signed-ranks test (for continuous variables). When use of formal testing to assess differences between users of the placebo VR and users of the dapivirine VR is required, the following methods will be used: for binomial response variables, chi-square tests and logistic regression (or exact testing methods); for continuous variables, t-tests and linear regression or nonparametric methods if data are non-Normal.

To assess the adequacy of the randomization, participants in each of the two arms will be compared for baseline characteristics including demographics and laboratory measurements using descriptive statistics.

Safety Endpoints

All females randomized into the study will be included in the primary analysis according to principle of Intent-to-Treat. To assess safety, the number and the percentages of participants experiencing each safety endpoint will be tabulated by study arm. Each participant will contribute once in each category (i.e., only for the highest severity AE for each participant) for the calculation of event rates. Exact binomial confidence intervals will be calculated for each safety endpoint for each arm and Fisher's exact test used to test for differences in event rates between the two arms.

10.8.3 Secondary Analyses

Acceptability

To assess acceptability of the study products, summary statistics will be calculated on each component of acceptability by arm.

Adherence

The average rate of VR use will be calculated in both arms along with 95% confidence intervals. These rates will be based on participant's self-report of product use at monthly clinic visits. The difference between adherence rates with its corresponding 95% confidence interval will be used to assess adherence of the study product compared to placebo.

Pharmacokinetics

A population mean and standard deviation of the end-of-period dapivirine concentrations for each woman in each 28-day period will be calculated based on the samples obtained as described above. The population mean from this study will be compared to the population mean and standard deviation from similar end of period dapivirine results for each matrix – plasma and vaginal fluid– in MTN-013/IPM 026, IPM 024, and IPM 013.

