2.6 Clinical Studies

2.6.1 Clinical Studies of Dapivirine Vaginal Rings

To date, 27 Phase 1 and Phase 1/2 clinical trials of dapivirine have been conducted: ⁵

- Eight trials of dapivirine VRs (25 mg and 200 mg loads) in which 469 participants were assigned to dapivirine VRs,
- Eight trials of dapivirine vaginal gel in which 491 participants used dapivirine vaginal gel,
- And, eleven trials of oral dapivirine among 211 participants.²

Efficacy and safety results from MTN-020 and IPM 027 will be made available to MTN-023 participants if the MTN-023 trial is still ongoing.

Clinical Pharmacokinetics

In all clinical trials of dapivirine vaginal rings and gels to date, dapivirine concentrations in plasma have been very low (less than 2 ng/mL) or undetectable after up to 84 days exposure. Plasma levels of dapivirine after vaginal exposure in clinical trials are 1000-fold lower than maximum plasma concentrations after oral administration of dapivirine (*e.g.* Cmax after 300 mg b.i.d. for 14 days was 2286 ng/mL). ⁵

The clinical pharmacokinetic profile of Ring-004 in IPM 013 showed a rapid increase in plasma and vaginal fluid concentrations of dapivirine after ring insertion, resulting in maximum concentrations in plasma by Day 7 and in vaginal fluids between Day 1 and Day 14, after which concentrations decreased steadily over the remainder of a 28-day or 35-day ring use period. Plasma dapivirine concentrations did not exceed 1 ng/mL,

and were therefore well below concentrations at the maximum tolerated dose (MTD) for multiple oral doses (300 mg b.i.d. for 14 days; plasma Cmax of 2286 ng/mL). For dapivirine in vaginal fluids, the highest concentration was observed in the area where the ring was placed, followed by the cervix, with the lowest concentrations near the introitus.

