Data from post-use analysis of residual levels of dapivirine in Ring-004 (IPM 015, in which a ring was inserted once every 28 days over a 12-week period) indicate that, on average, 4 mg of dapivirine were released over approximately one month of ring use. The mean amounts of dapivirine remaining in the used rings were similar for Weeks 4, 8 and 12 (post-insertion), at 21.09 mg, 21.54 mg and 21.84 mg, respectively. No clear relationship (neither linear nor exponential) was observed between the residual amount of dapivirine and corresponding plasma concentrations (*i.e.* at scheduled ring removal). It would appear that plasma concentrations below approximately 200 pg/mL were generally associated with above-average ring residual amounts, while the residual amounts appeared relatively constant (at levels between approximately 20 and 22 mg) for plasma concentrations above this value (200 pg/mL).

Safety

Trial Details		Number of Participants					
Trial Number	Description	Country	Ring-001 reservoir (200 mg)	Ring-002 reservoir (25 mg)	Ring-003 matrix* (25 mg)	Ring-004 matrix** (25 mg)	Placebo Ring
IPM 001	Safety and PK in women; 7 days	Belgium	12				12 (crossover)
IPM 008	Safety and PK in women; 7 days	Belgium		10			3
IPM 013	Safety and PK in women; 56/57 days	Belgium				36	12
IPM 015	Safety and PK in women; 84 days	Multiple Countries in Sub- Saharan Africa		-		140	140
IPM 018	Safety and PK in women; 28 days	Belgium		8	8		8
IPM 024	Safety and PK in women; 28 days	Belgium				8	8

Table 1: Clinical Phase I/II Trials of Dapivirine Vaginal Rings

Trial Details			Number of Participants					
Trial Number	Description	Country	Ring-001 reservoir (200 mg)	Ring-002 reservoir (25 mg)	Ring-003 matrix* (25 mg)	Ring-004 matrix** (25 mg)	Placebo Ring	
MTN-013/ IPM 026***	Safety and PK in women	United States				12	12	
IPM 028	Drug-drug Interaction (miconazole nitrate); 28 days	Belgium				36	0	
IPM 034	Safety and PK in women; 7, 14, 28, 56, or 84 days	Belgium				40	0	
TOTAL participants		12	18	8	172	195		

*Tin-catalyzed matrix ring.

**Platinum-catalyzed matrix ring

*** MTN-013/ IPM 026 was the first in human clinical trial of a vaginal ring containing maraviroc alone, dapivirine alone or a combination of the two (dapivirine/maraviroc) compared to placebo. The dapivirine VR arm included 12 participants. It should be noted, however, that the dapivirine VR was similar to Ring-004, but of slightly different composition.

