6.4.4 Retrieval of Study Product

Table 3: Retrieval of Study Product

	Retrieve Study Product
Permanent discontinuation or temporary hold	Within 24 hours
due to potential HIV seroconversion	
Permanent discontinuation for any other reason	Within 5 working days
or IoR discretion	
Temporary hold for reasons with expected	Within 7 working days
duration of greater than 7 days	
End of Study	Within 2 working days

If a product hold extends for 7 days or more, and product has not been retrieved as of the seventh day, study staff members must make every effort to retrieve study product as soon as possible.

It is not necessary to retrieve study products from participants for whom study product use is being temporarily held for less than 7 days. However, study products may be retrieved from such participants, to protect their safety, if there is concern that the participant may not comply with clinic staff instructions to refrain from study product use for the duration of the temporary hold.

For all study product holds requiring retrieval of study product(s), if the study product(s) are not retrieved within the timeframe stated in the table above, the MTN-023/IPM 030 PSRT must be informed.

The VR must be worn for approximately 28 consecutive days at a time and it is recommended not more than 35 days pass before the ring is replaced. If prolonged use of the study VR has occurred, attempts must be made to contact the participant and retrieve the study product.

For each participant, all VRs remaining in the participant's possession must be retrieved at the 24-Week (Final Clinic) Visit. If the participant does not bring her study product to this visit, study staff must arrange to retrieve the VR within 2 business days. If the VR(s) are not retrieved within that timeframe, the MTN-023/IPM 030 PSRT must be informed.

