10.4.2 Secondary Endpoints

Acceptability Endpoint

Acceptability of the study VR (dapivirine or placebo) in sexually experienced, HIVnegative adolescent females for 24 weeks will be determined by participants rating several components of acceptability (e.g., discreetness, likes and dislikes concerning the ring, attitude toward product characteristics, comfort and ease of use, partner reactions, and effect on sex) on a combination of categorical and continuous scales.

Adherence Endpoint

Adherence will be measured by the percentage of women who keep the VR inserted at all times in the vagina over the course of 24 weeks. A sample size of 96 women will provide an absolute precision of 9.1% (i.e., half the width of the 95% confidence interval) assuming an observed adherence of 75%.

Pharmacokinetic Endpoint

The PK endpoint is a description of the end of period (28 day post ring insertion) plasma and vaginal fluid dapivirine concentrations at week 2, 4, 12 and 24, and will be descriptively compared to the same results in a recently studied population of adult women (MTN-013/IPM 026). Plasma and vaginal fluid will also be collected at Week 2. The 28 day assessment in each ring period represents near steady-state concentrations in prior dapivirine ring studies. The intent is to determine if the plasma and vaginal fluid dapivirine concentrations are different in adolescent females compared to adult females 28 days after insertion of dapivirine vaginal rings. The vaginal fluid will be collected in 96 females.

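### The adolescent-versus-adult dapivirine comparison takes each woman's end-of-period sample with no condition on ring wear, so it mixes wear with absorption

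*Protocol*

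**What the plan says.** The pharmacokinetic paragraph of Protocol section 10.8.3 fixes the summary: "A population mean and standard deviation of the end-of-period dapivirine concentrations for each woman in each 28-day period will be calculated". It then fixes the comparison: "The population mean from this study will be compared to the population mean and standard deviation from similar end of period dapivirine results" in MTN-013/IPM 026, IPM 024 and IPM 013. Neither sentence refers to ring in place, removals, expulsions, product holds or actual days since insertion.

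Section 10.4.2 gives the purpose: "The intent is to determine if the plasma and vaginal fluid dapivirine concentrations are different in adolescent females compared to adult females", at 28 days after insertion. It supports that time point by stating that "The 28 day assessment in each ring period represents near steady-state concentrations in prior dapivirine ring studies".

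Other sections bear on how the samples arise:

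- Section 2.6.1 describes MTN-013/IPM 026 as 28 days of continuous ring use. It says that levels in IPM 013 peaked by Day 7 in plasma and between Day 1 and Day 14 in vaginal fluid, "after which concentrations decreased steadily over the remainder of a 28-day or 35-day ring use period".
- Section 6.4.4 allows some spread in wear time: "it is recommended not more than 35 days pass before the ring is replaced".
- Section 10.2 lists plasma and vaginal fluid concentrations both as the exposure endpoint and as an adherence endpoint.
- Wear is recorded through monthly questions and weekly text messages (7.8.1), and residual drug is measured in used rings (7.10). These data feed the adherence summary and an exploratory association (3.3), not the adult comparison.

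**The concern.** Two questions are folded into one mean: whether adolescents absorb or retain dapivirine differently from adults, and whether they wore the ring. Only the first matches the stated intent. Section 10.2 itself treats the concentrations as a marker of use, and section 2.6.1 reports that "plasma concentrations below approximately 200 pg/mL were generally associated with above-average ring residual amounts".

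The usual effect of non-wear is to pull the adolescent mean down. That can hide higher exposure in adolescents, which is the safety-relevant direction. It can also create an apparent deficit where exposure under equal wear is the same. Section 2.8.2 says that noted differences in drug levels may lead to further studies, so a misread comparison has a consequence.

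**Working it through.** **1. The protocol's own figure.** Section 10.4.2 gives 12 adults, 36 adolescents, CV 70%, 5% type I error and 80% power, and states a difference of 0.95 SD or 67%. Sidedness is not stated; I take two-sided. For a two-sample t-test the noncentrality is d × √(12 × 36 / 48) = 3d, with 46 degrees of freedom. Power at d = 0.95 is 79.7%, and 80% is reached at d = 0.954. Then 0.95 × 70% = 66.5%, or 67%. The figure reproduces. It contains no allowance for incomplete wear.

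**2. Effect on the mean.** Let s be the share of women with reduced levels and r the proportional cut. The adolescent mean is multiplied by k = 1 − s·r. A true 67% excess then appears as 1.67k − 1, and a true excess of 1/k − 1 appears as no difference.

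**3. Inputs not in the documents.** The cut r is not given, so I use 5% to 90%. For s I use two values:

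- 25%, borrowed from the adherence precision statement ("assuming an observed adherence of 75" per cent, for keeping the ring in at all times over 24 weeks).
- 8%, the complement of the 92% in IPM 015 who reported never having the ring out for more than an entire day (section 2.7.2).

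**4. Power.** Simulation, 100,000 runs: 12 adults with mean 1 and SD 0.70; 36 adolescents with mean 1.67 (or 1) and SD 0.70, of whom 9 (25%) or 3 (8%) have their values multiplied by 1 − r; two-sided 5% t-test.

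| Share affected | Cut r | k | True 67% excess appears as | Excess fully hidden | Power for true 67% excess | Equal exposure: chance of declaring adolescents lower |
|---|---|---|---|---|---|---|
| none | – | 1 | 67% | – | 80% | 2.5% |
| 25% | 5% | 0.9875 | 65% | 1% | 78% | 3% |
| 25% | 10% | 0.975 | 63% | 3% | 76% | 3% |
| 25% | 30% | 0.925 | 54% | 8% | 64% | 6% |
| 25% | 50% | 0.875 | 46% | 14% | 46% | 9% |
| 25% | 70% | 0.825 | 38% | 21% | 26% | 11% |
| 25% | 90% | 0.775 | 29% | 29% | 10% | 14% |
| 8% | 50% | 0.96 | 60% | 4% | 70% | 4% |

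If the number affected varies at random around 9 instead of being fixed, the 90% row gives 14% and the 70% row 28%; the other rows barely move.

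**5. Model caveat.** Holding SD at 0.70 while the mean rises to 1.67 implies an adolescent CV of 0.70 / 1.67 = 42%. With 70% CV in both groups, power without any non-wear is already only about 43%. The 80% starting point therefore belongs to the constant-SD model, which is the one that reproduces the protocol's figure.

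**6. The opposite direction.** Because levels peak early and then fall, a ring re-inserted shortly before the visit could read high. If the affected 25% read 25% or 50% higher, k is 1.0625 or 1.125.

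**The case against.** Several points on the other side are sound.

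- **Analysis-plan detail.** Evaluability rules for PK samples often sit in a statistical analysis plan, and none is shown. But 10.8.3 does not leave the set open; it names each woman in each period. A later plan would have to narrow that text.
- **Stray samples.** A reader might infer that Early Termination samples on arbitrary days are certainly averaged in. Section 10.4.2 defines the endpoint as end of period, 28 days after insertion, which argues against that. The sample in 7.5.1 to 7.5.4 is taken at the visit where product is discontinued, and PK sampling then stops. The main issue is women who stay on product with partial wear.
- **The 75%.** It is a planning value for a confidence interval, and one brief removal in 24 weeks fails the definition. Reading it as a quarter of women with large cuts at the sampled time point is not supported; many cuts may be near zero.
- **Direction.** A reader might infer that non-wear must lower the level. The early peak and later decline in 2.6.1 do not support that.
- **Residual drug.** Just before the sentence on low plasma levels, 2.6.1 reports no clear relationship between residual amount and plasma concentration. Residual drug also measures release, so filtering on it could select on exposure itself.
- **Descriptive intent.** Section 10.4.2 calls the comparison descriptive, and exposure under actual use is a legitimate answer to the exposure objective. The same section nevertheless gives a power statement and an intent to determine whether levels differ.

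What remains is that the stated rule does not separate wear from absorption, and the data to do so are not linked to the comparison.

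**Conclusion.** The point holds as a mismatch between the stated aim and the fixed analysis. Incomplete wear will tend to, but need not, lower the adolescent mean.

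The size cannot be read from the documents. With 25% affected, it runs from negligible (5% cut: mean down 1.25%, power about 78%) to severe (90% cut: mean down 22.5%, power about 10%). With 8% affected and a 50% cut, power is about 70%. All of these power figures rest on the constant-SD model and on assumed cuts.

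A reader might also infer that the steady-state sentence is plainly wrong. The documents do not settle this. It could mean late, slowly changing levels that repeat across ring periods, which the similar mean residual amounts at Weeks 4, 8 and 12 in IPM 015 would fit. It does sit badly with the steady decline in 2.6.1, and the two passages need reconciling.

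**What to change.** In section 10.8.3:

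1. Keep the all-samples mean and label it as exposure under actual use.
2. Add a prespecified like-for-like adult comparison. Limit it to samples taken with the ring in place, with actual days since insertion inside the 28-day visit window, and with no reported removal or expulsion beyond a limit that the protocol states.
3. Use residual drug only as a supportive sensitivity check, not as an inclusion filter.

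In section 10.4.2, reconcile the steady-state sentence with the decline described in 2.6.1.

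The change is to wording only: rings are inserted at scheduled visits, and removals, expulsions and residual drug are already collected. There are two costs. The like-for-like set is smaller: at 75% adherence, about 0.75 × 36 = 27 of the weighed-swab women. And the published adult means cannot be filtered in the same way, so the comparison improves on the adolescent side only. Reporting both results side by side keeps that visible.

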10.8.4 Missing Data

In any situation with missing data, an appropriate secondary analysis will be performed to adjust for variables that may be related to the missingness mechanism. If missing data rates are higher than 10%, covariates that are related to missingness in likelihoodbased regression models will be included. A sensitivity analysis to assess the potential impact of the missing data will also be performed. This analysis will include imputing the data under the most extreme scenarios of information missingness, such as assuming everyone missing has an extreme value of the missing variable, as well as less informative imputation approaches.

11 DATA HANDLING AND RECORDKEEPING

11.1 Data Management Responsibilities

CRFs will be developed by the MTN SDMC in conjunction with the protocol team. Quality control reports and queries routinely will be generated and distributed by the SDMC to the study sites for verification and resolution. As part of the study activation process, each study site must identify all CRFs to be used as source documents. Data are transferred to the MTN SDMC, entered, and cleaned using the DataFax data management system.

11.2 Source Documents and Access to Source Data/Documents

All study sites will maintain source data/documents in accordance with current DAIDS policies.

(http://www.niaid.nih.gov/labsandresources/resources/daidsclinrsrch/Pages/Default.asp x) Each IoR/designee will maintain, and store securely, complete, accurate and current study records throughout the study. In accordance with U.S. regulations regarding testing investigational products, the IoR/designee will maintain all study documentation for at least two years following the date of marketing approval for the study product being tested for the indication in which they were studied. If no marketing application is filed, or if the application is not approved, the records will be retained for two years after the investigation is discontinued and the US FDA is notified.

Study records must be maintained on site for the entire period of study implementation. Thereafter, instructions for record storage will be provided by DAIDS. No study records may be moved to an off-site location or destroyed prior to receiving approval from DAIDS.

